12.3. Appendix 3: Study Governance Considerations

Regulatory and Ethical Considerations

- This study will be conducted in accordance with the protocol and with:
 - Consensus ethical principles derived from international guidelines including the Declaration of Helsinki and Council for International Organizations of Medical Sciences (CIOMS) International Ethical Guidelines
 - Applicable ICH Good Clinical Practice (GCP) Guidelines
 - Applicable laws and regulations
- The protocol, protocol amendments, ICF, Investigator Brochure, and other relevant documents (eg, advertisements) must be submitted to an IRB/IEC by the investigator and reviewed and approved by the IRB/IEC before the study is initiated.
- Any amendments to the protocol will require IEC/IRB approval before implementation of changes made to the study design, except for changes necessary to eliminate an immediate hazard to study participants.
- The investigator will be responsible for the following:
 - Providing written summaries of the status of the study to the IRB/IEC annually or more frequently in accordance with the requirements, policies, and procedures established by the IRB/EC
 - Notifying the IRB/IEC of SAE or other significant safety findings as required by IRB/IEC procedures
 - Providing oversight of the conduct of the study at the site and adherence to requirements of 21 CFR, ICH guidelines, the IRB/IEC, European regulation 536/2014 for clinical studies (if applicable), and all other applicable local regulations

Financial Disclosure

Investigators and sub-investigators will provide the sponsor with sufficient, accurate financial information as requested to allow the sponsor to submit complete and accurate financial certification or disclosure statements to the appropriate regulatory authorities. Investigators are responsible for providing information on financial interests during the course of the study and for 1 year after completion of the study.

Informed Consent Process

- The investigator or his/her representative will explain the nature of the study to the participant or his/her legally authorized representative and answer all questions regarding the study.
- Participants must be informed that their participation is voluntary. Participants or their legally authorized representative will be required to sign a statement of

informed consent that meets the requirements of 21 CFR 50, local regulations, ICH guidelines, Health Insurance Portability and Accountability Act (HIPAA) requirements, where applicable, and the IRB/IEC or study center.

- The medical record must include a statement that written informed consent was obtained before the participant was enrolled in the study and the date the written consent was obtained. The authorized person obtaining the informed consent must also sign the ICF.
- Participants must be re-consented to the most current version of the ICF(s) during their participation in the study.
- A copy of the ICF(s) must be provided to the participant or the participant's legally authorized representative.
- Participants who are rescreened are required to sign a new ICF.

The ICF may contain a separate section that addresses the use of remaining mandatory samples for optional exploratory research in accordance with SOP-GSKF-410. The investigator or authorized designee will explain to each participant the objectives of the exploratory research. Participants will be told that they are free to refuse to participate and may withdraw their consent at any time and for any reason during the storage period. A separate signature will be required to document a participant's agreement to allow any remaining specimens to be used for exploratory research. Participants who decline to participate will not provide this separate signature.

Data Protection

- Participants will be assigned a unique identifier by the sponsor. Any participant records or datasets that are transferred to the sponsor will contain the identifier only; participant names or any information which would make the participant identifiable will not be transferred.
- The participant must be informed that his/her personal study-related data will be used by the sponsor in accordance with local data protection law. The level of disclosure must also be explained to the participant.
- The participant must be informed that his/her medical records may be examined by Clinical Quality Assurance auditors or other authorized personnel appointed by the sponsor, by appropriate IRB/IEC members, and by inspectors from regulatory authorities.

Publication Policy

- The results of this study may be published or presented at scientific meetings. If this is foreseen, the investigator agrees to submit all manuscripts or abstracts to the sponsor before submission. This allows the sponsor to protect proprietary information and to provide comments.
- The sponsor will comply with the requirements for publication of study results. In accordance with standard editorial and ethical practice, the sponsor will generally support publication of multicenter studies only in their entirety and

not as individual site data. In this case, a coordinating investigator will be designated by mutual agreement.

- Authorship will be determined by mutual agreement and in line with International Committee of Medical Journal Editors authorship requirements.

Dissemination of Clinical Study Data

Where required by applicable regulatory requirements, an investigator signatory will be identified for the approval of the clinical study report. The investigator will be provided reasonable access to statistical tables, figures, and relevant reports and will have the opportunity to review the complete study results at a GSK site or other mutually-agreeable location.

GSK will also provide the investigator with the full summary of the study results. The investigator is encouraged to share the summary results with the study participants, as appropriate.

GSK will provide the investigator with the randomization codes for their site only after completion of the full statistical analysis.

The procedures and timing for public disclosure of the results summary and for development of a manuscript for publication will be in accordance with GSK Policy 408.

Data Quality Assurance

- All participant data relating to the study will be recorded on printed or electronic CRF unless transmitted to the sponsor or designee electronically (eg, laboratory data). The investigator is responsible for verifying that data entries are accurate and correct by physically or electronically signing the CRF.
- The investigator must maintain accurate documentation (source data) that supports the information entered in the CRF.
- The investigator must permit study-related monitoring, audits, IRB/IEC review, and regulatory agency inspections and provide direct access to source data documents.
- The sponsor or designee is responsible for the data management of this study including quality checking of the data.
- Study monitors will perform ongoing source data verification to confirm that data entered into the CRF by authorized site personnel are accurate, complete, and verifiable from source documents; that the safety and rights of participants are being protected; and that the study is being conducted in accordance with the currently approved protocol and any other study agreements, ICH GCP, and all applicable regulatory requirements.
- Records and documents, including signed ICF, pertaining to the conduct of this study must be retained by the investigator for 7 years after study completion unless local regulations or institutional policies require a longer retention period. No records may be destroyed during the retention period without the

written approval of the sponsor. No records may be transferred to another location or party without written notification to the sponsor.

Source Documents

- Source documents provide evidence for the existence of the participant and substantiate the integrity of the data collected. Source documents are filed at the investigator's site.
- Data reported on the CRF or entered in the eCRF that are transcribed from source documents must be consistent with the source documents or the discrepancies must be explained. The investigator may need to request previous medical records or transfer records, depending on the study. Also, current medical records must be available.
- Definition of what constitutes source data can be found in the Trial Master File.

Study and Site Closure

GSK or its designee reserves the right to close the study site or terminate the study at any time for any reason at the sole discretion of GSK. Study sites will be closed upon study completion. A study site is considered closed when all required documents and study supplies have been collected and a study-site closure visit has been performed.

The investigator may initiate study-site closure at any time, provided there is reasonable cause and sufficient notice is given in advance of the intended termination.

Reasons for the early closure of a study site by the sponsor or investigator may include but are not limited to:

- Failure of the investigator to comply with the protocol, the requirements of the IRB/IEC or local health authorities, the sponsor's procedures, or GCP guidelines
- Inadequate recruitment of participants by the investigator
- Discontinuation of further study treatment development

12.4. Appendix 4: Liver Safety: Required Actions and Follow-up Assessments

Liver chemistry stopping and increased monitoring criteria have been designed to assure subject safety and evaluate liver event aetiology (in alignment with the FDA premarketing clinical liver safety guidance).

<http://www.fda.gov/downloads/Drugs/GuidanceComplianceRegulatoryInformation/Guidances/UCM174090.pdf>.

Liver chemistry stopping criteria and required follow up assessments

Liver Chemistry Stopping Criteria – Liver Stopping Event	
ALT-absolute	ALT \geq 8xULN
ALT Increase	ALT \geq 5xULN persists for \geq 2 weeks
ALT Increase	ALT \geq 3xULN persists for \geq 4 weeks
Bilirubin^{1,2}	ALT \geq 3xULN and bilirubin \geq 2xULN (>35% direct bilirubin)
INR²	ALT \geq 3xULN and INR>1.5, if INR measured
Cannot Monitor	ALT \geq 3xULN and cannot be monitored weekly for 4 weeks
Symptomatic³	ALT \geq 3xULN associated with symptoms (new or worsening) believed to be related to liver injury or hypersensitivity

Required Actions and Follow up Assessments following ANY Liver Stopping Event

Actions	Follow Up Assessments

 • Immediately discontinue study treatment • Report the event to GSK within 24 hours • Complete the liver event CRF and complete an SAE data collection tool if the event also meets the criteria for an SAE² • Perform liver event follow up assessments • Monitor the subject until liver chemistries resolve, stabilize, or return to within baseline (see MONITORING below) • Do not restart/rechallenge subject with study treatment unless allowed per protocol and GSK Medical Governance approval is granted. • If restart/rechallenge not allowed per protocol 	
 • Viral hepatitis serology⁴ • Blood sample for pharmacokinetic (PK) analysis, obtained within 14 days after last dose⁵ • Serum creatine phosphokinase (CPK) and lactate dehydrogenase (LDH). • Fractionate bilirubin, if total bilirubin \geq 2xULN • Obtain complete blood count with differential to assess eosinophilia • Record the appearance or worsening of clinical symptoms of liver injury, or hypersensitivity, on the AE report form


or not granted, permanently discontinue study treatment and may continue subject in the study for any protocol specified follow up assessments
 
MONITORING:
 
For bilirubin or INR criteria:
 
 Repeat liver chemistries (include ALT, AST, alkaline phosphatase, bilirubin) and perform liver event follow up assessments within 24 hrs Monitor subjects twice weekly until liver chemistries resolve, stabilize or return to within baseline A specialist or hepatology consultation is recommended 
For All other criteria:
 
 Repeat liver chemistries (include ALT, AST, alkaline phosphatase, bilirubin) and perform liver event follow up assessments within 24-72 hrs Monitor subjects weekly until liver chemistries resolve, stabilize or return to within baseline 	
 Record use of concomitant medications on the concomitant medications report form including acetaminophen, herbal remedies, other over the counter medications. Record alcohol use on the liver event alcohol intake case report form 
For bilirubin or INR criteria:
 
 Anti-nuclear antibody, anti-smooth muscle antibody, Type 1 anti-liver kidney microsomal antibodies, and quantitative total immunoglobulin G (IgG or gamma globulins). Serum acetaminophen adduct HPLC assay (quantifies potential acetaminophen contribution to liver injury in subjects with definite or likely acetaminophen use in the preceding week [James, 2009]). Liver imaging (ultrasound, magnetic resonance, or computerised tomography) and /or liver biopsy to evaluate liver disease: complete Liver Imaging and/or Liver Biopsy CRF forms.
--	--

1. Serum bilirubin fractionation should be performed if testing is available. If serum bilirubin fractionation is not immediately available, discontinue study treatment for that subject if $ALT \geq 3 \times ULN$ **and** bilirubin $\geq 2 \times ULN$. Additionally, if serum bilirubin fractionation testing is unavailable, **record presence of detectable urinary bilirubin on dipstick**, indicating direct bilirubin elevations and suggesting liver injury.
2. All events of $ALT \geq 3 \times ULN$ **and** bilirubin $\geq 2 \times ULN$ ($>35\%$ direct bilirubin) or $ALT \geq 3 \times ULN$ **and** INR >1.5 , if INR measured which may indicate severe liver injury (possible 'Hys Law'), **must be reported as an SAE (excluding studies of hepatic impairment or cirrhosis)**; INR measurement is not required and the threshold value stated will not apply to subjects receiving anticoagulants
3. New or worsening symptoms believed to be related to liver injury (such as fatigue, nausea, vomiting, right upper quadrant pain or tenderness, or jaundice) or believed to be related to hypersensitivity (such as fever, rash or eosinophilia)
4. Includes: Hepatitis A IgM antibody; Hepatitis B surface antigen and Hepatitis B Core Antibody (IgM); Hepatitis C RNA; Cytomegalovirus IgM antibody; Epstein-Barr viral capsid antigen IgM antibody (or if unavailable, obtain heterophile antibody or monospot testing); Hepatitis E IgM antibody
5. PK sample may not be required for subjects known to be receiving placebo or non-GSK comparator treatments.) Record the date/time of the PK blood sample draw and the date/time of the last dose of study treatment prior to blood sample draw on the CRF. If the date or time of the last dose is unclear, provide the subject's best approximation. If the date/time of the last dose cannot be approximated OR a PK sample cannot be collected in the time period indicated above, do not obtain a PK sample. Instructions for sample handling and shipping are in the SRM.

Liver chemistry increased monitoring criteria with continued therapy

Liver Chemistry Increased Monitoring Criteria – Liver Monitoring Event	
Criteria	Actions
ALT \geq 3xULN and <5xULN and bilirubin <2xULN, without symptoms believed to be related to liver injury or hypersensitivity, and who can be monitored weekly for 4 weeks	
 Notify the GSK medical monitor within 24 hours of learning of the abnormality to discuss subject safety. Subject can continue study treatment Subject must return weekly for repeat liver chemistries (ALT, AST, alkaline phosphatase, bilirubin) until they resolve, stabilise or return to within baseline If at any time subject meets the liver chemistry stopping criteria, proceed as described above If, after 4 weeks of monitoring, ALT <3xULN and bilirubin <2xULN, monitor subjects twice monthly until liver chemistries normalize or return to within baseline.
ALT \geq 5xULN and <8xULN and bilirubin <2xULN, without symptoms believed to be related to liver injury or hypersensitivity, and who can be monitored weekly for 2 weeks	
 Notify the GSK medical monitor within 24 hours of learning of the abnormality to discuss subject safety. Subject can continue study treatment Subject must return 2-3 days after the initial observation and then return every 2-4 days for repeat liver chemistries (ALT, AST, alkaline phosphatase, bilirubin) until they resolve, stabilise or return to within baseline If at any time subject meets the liver chemistry stopping criteria, proceed as described above If, after 2 weeks of monitoring, ALT <5xULN and bilirubin <2xULN, monitor subjects twice monthly until liver chemistries normalize or return to within baseline.

References

12.5. Appendix 5: Adverse Events: Definitions and Procedures for Recording, Evaluating, Follow-up, and Reporting

Definition of AE

AE Definition

• An AE is any untoward medical occurrence in a clinical study participant, temporally associated with the use of a study treatment, whether or not considered related to the study treatment.• NOTE: An AE can therefore be any unfavorable and unintended sign (including an abnormal laboratory finding), symptom, or disease (new or exacerbated) temporally associated with the use of a study treatment.

Events Meeting the AE Definition


• Any abnormal laboratory test results (hematology, clinical chemistry, or urinalysis) or other safety assessments (e.g., ECG, radiological scans, vital signs measurements), including those that worsen from baseline, considered clinically significant in the medical and scientific judgment of the investigator (i.e., not related to progression of underlying disease).• Exacerbation of a chronic or intermittent pre-existing condition including either an increase in frequency and/or intensity of the condition.• New conditions detected or diagnosed after study treatment administration even though it may have been present before the start of the study.• Signs, symptoms, or the clinical sequelae of a suspected drug-drug interaction.• Signs, symptoms, or the clinical sequelae of a suspected overdose of either study treatment or a concomitant medication. Overdose per se will not be reported as an AE/SAE unless it is an intentional overdose taken with possible suicidal/self-harming intent. Such overdoses should be reported regardless of sequelae.• "Lack of efficacy" or "failure of expected pharmacological action" per se will not be reported as an AE or SAE. Such instances will be captured in the efficacy assessments. However, the signs, symptoms, and/or clinical sequelae resulting from lack of efficacy will be reported as AE or SAE if they fulfil the definition of an AE or SAE.
--

Events NOT Meeting the AE Definition

• Any clinically significant abnormal laboratory findings or other abnormal safety assessments which are associated with the underlying disease, unless judged by the investigator to be more severe than expected for the participant's condition.• The disease/disorder being studied or expected progression, signs, or symptoms of

the disease/disorder being studied, unless more severe than expected for the participant's condition.
 
 • Medical or surgical procedure (eg, endoscopy, appendectomy): the condition that leads to the procedure is the AE. • Situations in which an untoward medical occurrence did not occur (social and/or convenience admission to a hospital). • Anticipated day-to-day fluctuations of pre-existing disease(s) or condition(s) present or detected at the start of the study that do not worsen.

Definition of SAE

If an event is not an AE per definition above, then it cannot be an SAE even if serious conditions are met (eg, hospitalization for signs/symptoms of the disease under study, death due to progression of disease).

A SAE is defined as any untoward medical occurrence that, at any dose:
a. Results in death
b. Is life-threatening
The term 'life-threatening' in the definition of 'serious' refers to an event in which the participant was at risk of death at the time of the event. It does not refer to an event, which hypothetically might have caused death, if it were more severe.
c. Requires inpatient hospitalization or prolongation of existing hospitalization
In general, hospitalization signifies that the participant has been detained (usually involving at least an overnight stay) at the hospital or emergency ward for observation and/or treatment that would not have been appropriate in the physician's office or outpatient setting. Complications that occur during hospitalization are AE. If a complication prolongs hospitalization or fulfils any other serious criteria, the event is serious. When in doubt as to whether "hospitalization" occurred or was necessary, the AE should be considered serious.
Hospitalization for elective treatment of a pre-existing condition that did not worsen from baseline is not considered an AE.
d. Results in persistent disability/incapacity

 • The term disability means a substantial disruption of a person's ability to conduct normal life functions. • This definition is not intended to include experiences of relatively minor medical significance such as uncomplicated headache, nausea, vomiting, diarrhea, influenza, and accidental trauma (eg, sprained ankle) which may interfere with or prevent everyday life functions but do not constitute a substantial disruption.
e. Is a congenital anomaly/birth defect

f. Other situations:

- Medical or scientific judgment should be exercised in deciding whether SAE reporting is appropriate in other situations such as important medical events that may not be immediately life-threatening or result in death or hospitalization but may jeopardize the participant or may require medical or surgical intervention to prevent one of the other outcomes listed in the above definition. These events should usually be considered serious.

Examples of such events include invasive or malignant cancers, intensive treatment in an emergency room or at home for allergic bronchospasm, blood dyscrasias or convulsions that do not result in hospitalization, or development of drug dependency or drug abuse.

g. Is associated with liver injury and impaired liver function defined as:

- ALT \geq 3xULN and total bilirubin* \geq 2xULN ($>35\%$ direct), **or**
- ALT \geq 3xULN and INR** > 1.5 .

* Serum bilirubin fractionation should be performed if testing is available; if unavailable, measure urinary bilirubin via dipstick. If fractionation is unavailable and ALT \geq 3xULN and total bilirubin \geq 2xULN, then the event is still to be reported as an SAE.

- ** INR testing not required per protocol and the threshold value does not apply to participants receiving anticoagulants. If INR measurement is obtained, the value is to be recorded on the SAE form.

Recording AE and SAE**AE and SAE Recording**

- When an AE/SAE occurs, it is the responsibility of the investigator to review all documentation (eg, hospital progress notes, laboratory, and diagnostics reports) related to the event.
- The investigator will then record all relevant AE/SAE information in the CRF.
- It is **not** acceptable for the investigator to send photocopies of the participant's medical records to GSK in lieu of completion of the GSK /AE/SAE CRF page.
- There may be instances when copies of medical records for certain cases are requested by GSK. In this case, all participant identifiers, with the exception of the participant number, will be redacted on the copies of the medical records before submission to GSK.
- The investigator will attempt to establish a diagnosis of the event based on signs, symptoms, and/or other clinical information. Whenever possible, the diagnosis (not the individual signs/symptoms) will be documented as the AE/SAE.

Assessment of Intensity

The investigator will make an assessment of intensity for each AE and SAE reported during the study and assign it to 1 of the following categories:

- Mild: An event that is easily tolerated by the participant, causing minimal discomfort and not interfering with everyday activities.
- Moderate: An event that causes sufficiently discomfort and interferes with normal everyday activities.
- Severe: An event that prevents normal everyday activities. An AE that is assessed as severe should not be confused with an SAE. Severe is a category utilized for rating the intensity of an event; and both AE and SAE can be assessed as severe.

An event is defined as 'serious' when it meets at least 1 of the predefined outcomes as described in the definition of an SAE, NOT when it is rated as severe.

Assessment of Causality

- The investigator is obligated to assess the relationship between study treatment and each occurrence of each AE/SAE.
- A "reasonable possibility" of a relationship conveys that there are facts, evidence, and/or arguments to suggest a causal relationship, rather than a relationship cannot be ruled out.
- The investigator will use clinical judgment to determine the relationship.
- Alternative causes, such as underlying disease(s), concomitant therapy, and other risk factors, as well as the temporal relationship of the event to study treatment administration will be considered and investigated.
- The investigator will also consult the Investigator's Brochure (IB) and/or Product Information, for marketed products, in his/her assessment.
- For each AE/SAE, the investigator **must** document in the medical notes that he/she has reviewed the AE/SAE and has provided an assessment of causality.
- There may be situations in which an SAE has occurred and the investigator has minimal information to include in the initial report to GSK. However, **it is very important that the investigator always make an assessment of causality for every event before the initial transmission of the SAE data to GSK.**
- The investigator may change his/her opinion of causality in light of follow-up information and send an SAE follow-up report with the updated causality assessment.
- The causality assessment is one of the criteria used when determining regulatory reporting requirements.

Follow-up of AE and SAE

- The investigator is obligated to perform or arrange for the conduct of supplemental measurements and/or evaluations as medically indicated or as requested by GSK to elucidate the nature and/or causality of the AE or SAE as fully as possible. This may include additional laboratory tests or investigations, histopathological examinations, or consultation with other health care professionals.
- If a participant dies during participation in the study or during a recognized follow-up period, the investigator will provide GSK with a copy of any post-mortem findings including histopathology.
- New or updated information will be recorded in the originally completed CRF.
- The investigator will submit any updated SAE data to GSK within 24 hours of receipt of the information.

Reporting of SAE to GSK**SAE Reporting to GSK via Electronic Data Collection Tool**

- The primary mechanism for reporting SAE to GSK will be the electronic data collection tool.
- If the electronic system is unavailable for more than 24 hours, then the site will use the paper SAE data collection tool (see next section).
- The site will enter the SAE data into the electronic system as soon as it becomes available.
- After the study is completed at a given site, the electronic data collection tool will be taken off-line to prevent the entry of new data or changes to existing data.
- If a site receives a report of a new SAE from a study participant or receives updated data on a previously reported SAE after the electronic data collection tool has been taken off-line, then the site can report this information on a paper SAE form (see next section) or to the medical monitor/SAE coordinator by telephone.
- Contacts for SAE reporting can be found in the study reference manual.

SAE Reporting to GSK via Paper CRF

- Facsimile transmission of the SAE paper CRF is the preferred method to transmit this information to the **medical monitor or the SAE coordinator**.
- In rare circumstances and in the absence of facsimile equipment, notification by telephone is acceptable with a copy of the SAE data collection tool sent by overnight mail or courier service.
- Initial notification via telephone does not replace the need for the investigator to complete and sign the SAE CRF pages within the designated reporting time frames.
- Contacts for SAE reporting can be found in the study reference manual.

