6.2. Exclusion Criteria

Participants are excluded from the study if any of the following criteria apply:

Medical Conditions

1. Participants with a history of myocardial infarction, angina, congestive heart failure exacerbation, hospitalization for cardiac aetiology, stroke or transient ischemic attack in the past 12 months.
2. Neurologic, musculoskeletal, osteoarthritis, or any other condition that in the opinion of the investigator limits participant's ability to complete study physical assessments.
3. Current or chronic history of liver disease, or known hepatic or biliary abnormalities (with the exception of Gilbert's syndrome or asymptomatic gallstones).
4. Participants with a history of cholecystectomy.
5. Participants with a history of malignancy that is not in complete remission for at least 2 years or 1 year for non-melanoma skin carcinoma.
6. Participants with a family history of early onset prostate cancer or familial prostate cancer (multiple family members).

7. Diseases known to cause malabsorption of protein or energy, such as inflammatory bowel disease, celiac disease, pancreatic insufficiency, etc.

Prior/Concomitant Therapy

8. Current or planned administration of cholestyramine or strong oral or injectable cytochrome P-450 isoenzyme 3A4 (CYP3A4) inducers (refer to Section 7.7 for a list of prohibited medications).
9. Current or planned use of any prescription drugs known to affect muscle mass, including androgen supplements, anti-androgens (such as LHRH agonists), anti-estrogens (tamoxifen, etc.), recombinant growth hormone, megestrol, etc.
10. Use of oral steroids concurrently or within 4 weeks preceding the screening visit.

Prior/Concurrent Clinical Study Experience

11. The participant has participated in a clinical trial and has received an investigational product within the following time period prior to randomization in the current study: 30 days, 5 half-lives or twice the duration of the biological effect of the investigational product (whichever is longer).

Diagnostic assessments

12. Participants with values outside the specified ranges for the following Key Clinical Laboratory Tests must be excluded from the study:
 - Renal function: Glomerular Filtration Rate (GFR) <30 (mL/min/1.73 m²) using formulae provided in the Study Reference Manual (SRM). Note: Participants receiving dialysis are excluded from this study.
 - Metabolic – HbA1c $>7.5\%$.

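### Appendix 4's liver tables leave one ALT/bilirubin combination with no stated action and give two monitoring frequencies when ALT falls from 5-8xULN to 3-5xULN

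*Protocol*

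**What the plan says.** Protocol Section 12.4 (Appendix 4) sets out two tables.

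- **Stopping table.** The bilirubin row needs ALT ≥3xULN and bilirubin ≥2xULN, qualified by ">35% direct bilirubin". Footnote 1 drops that qualifier in one circumstance: "If serum bilirubin fractionation is not immediately available, discontinue study treatment for that subject if" ALT is ≥3xULN and bilirubin ≥2xULN. The other rows are ALT ≥8xULN; ALT ≥5xULN lasting 2 weeks or more; ALT ≥3xULN lasting 4 weeks or more; and ALT ≥3xULN with INR above 1.5 (if measured), with relevant symptoms, or in someone who cannot attend weekly for 4 weeks.
- **Monitoring table**, titled "Liver chemistry increased monitoring criteria with continued therapy". The first row covers ALT ≥3xULN "and <5xULN and bilirubin <2xULN, without symptoms believed to be related to liver injury or hypersensitivity", in a participant who can attend weekly for 4 weeks. The medical monitor is told within 24 hours and "Subject must return weekly for repeat liver chemistries". Twice-monthly checks are allowed only after 4 weeks and with ALT below 3xULN. The second row covers ALT from 5 to below 8xULN with the same bilirubin and symptom limits and 2 weeks of availability. It has the same 24-hour call, a test at 2-3 days and then every 2-4 days, and finally: "If, after 2 weeks of monitoring, ALT <5xULN and bilirubin <2xULN, monitor subjects twice monthly".

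In Section 6.2, exclusion 3 makes an exception for Gilbert's "syndrome or asymptomatic gallstones". Exclusion 12 accepts isolated bilirubin above 1.5xULN if it is fractionated and less than 35% direct. Section 9.5.4 separately asks for repeat testing of values judged clinically significantly abnormal.

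**The concern.** The two tables should together assign every participant with ALT ≥3xULN to one action, and they do not.

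(a) The stopping row excludes a low direct fraction, while both monitoring rows exclude bilirubin ≥2xULN whatever the fraction. Raised ALT with high, largely indirect bilirubin therefore falls between them, and it carries less mandated action than the same ALT with lower bilirubin.

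(b) The two monitoring rows step down at different ALT levels, and no text says which governs a participant who moves from one band to the other.

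Liver enzyme elevation is the first entry in the protocol's risk table, which reports transient ALT rises in Phase 1b, and safety is a primary objective. Sites could handle the same chemistry differently. Because the entry criteria admit Gilbert's syndrome and isolated indirect bilirubin elevation, case (a) is foreseeable, although those criteria do not admit anyone with ALT already at 3xULN together with raised bilirubin.

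**Working it through.** The plan states no figure to reproduce. The check applies each row to defined states.

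**(a) Gap.** Test state: ALT 4xULN, bilirubin 2.2xULN, 20% direct, no symptoms, INR not measured, weekly attendance possible for 4 weeks, first detection.

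- ALT ≥8xULN: 4 < 8, not met.
- Both persistence rows: week 0, not met.
- Bilirubin row: 4 ≥ 3 and 2.2 ≥ 2, but 20% is not above 35%, so not met.
- INR, symptom and Cannot Monitor rows: not met.
- Monitoring row 3 to <5xULN: ALT fits, but 2.2 is not < 2, so not met.
- Monitoring row 5 to <8xULN: neither ALT nor bilirubin fits.

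No row applies. Changing only the bilirubin result:

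| Bilirubin (xULN) | Direct fraction | Appendix 4 action at ALT 4xULN |
|---|---|---|
| 1.9 | any | call within 24 hours, weekly tests |
| 2.2 | 20%, measured | none stated |
| 2.2 | not immediately available | stop (footnote 1) |
| 2.2 | 40%, measured | stop |

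To find the limits of the gap, the rows were applied at first detection to a grid: 7 ALT values (3 to 10xULN) × 4 bilirubin values (1 to 3xULN) × 5 direct-fraction states (unavailable, 10, 35, 36, 60%) × 3 INR states (unmeasured, 1.0, 1.6) × 2 symptom states × 4 lengths of possible weekly attendance (0, 2, 3, 4 weeks) = 3,360 states.

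- Stopping table only: 2,990.
- Monitoring table only: 100.
- Both tables: 230.
- Neither table: 40.

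The 40 are 5 ALT values (3, 4, 5, 6, 7.9) × 2 bilirubin values (2, 3) × 2 fractions (10%, 35%) × 2 INR states (unmeasured, 1.0), all without symptoms and with 4 weeks' attendance possible. No other type of state is unassigned. These counts describe the grid, not how often patients would be affected. The gap ends once ALT ≥5xULN has lasted 2 weeks or ALT ≥3xULN has lasted 4 weeks.

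**(b) Conflict.** Test state: ALT 6xULN at day 0 and 4.5xULN at day 14, bilirubin 1xULN, no symptoms, weekly attendance possible.

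- Step-down of the 5-8xULN row: 4.5 < 5 and 1 < 2, so twice-monthly checks. Taking that as every 14 days, the next test is day 28.
- 3-5xULN row: 3 ≤ 4.5 < 5 and 1 < 2, so weekly checks, with the next tests on days 21 and 28. Its own step-down fails on both counts: 14 days is less than 28, and 4.5 is not below 3.
- Four-week persistence stop: ALT has been ≥3xULN for 14 of the 28 days. On the 14-day schedule the next test falls on the day that limit is reached.

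The conflict arises for ALT from 3 to below 5xULN at week 2, because the step-down has no lower ALT bound.

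**The case against.** **Other safeguards exist.** A reader might infer that gap participants stay on drug with no repeat test. The documents do not support that. Section 9.5.4 calls for repeats of values judged clinically significantly abnormal, Section 9 sends immediate safety concerns to the sponsor, unscheduled visits can include liver chemistry, and the persistence stops can apply later. This stands, and it limits the harm. But Section 9.5.4 rests on investigator judgement and sets no interval, no call to the medical monitor and no treatment decision, so it does not fill the cell.

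**Length of delay.** A reader might also expect a 25 to 39 day wait (85 − 60 and 91 − 52, from the Day 56 and Day 90 windows, with no chemistry scheduled at Day 80). That is only the longest on-treatment interval between scheduled draws. Between Day 14 and Day 28 it is 8 to 20 days (24 − 16 and 32 − 12), and Section 9.5.4 may shorten either.

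**Overlap with stopping.** At ALT 6xULN, someone able to attend weekly for 2 weeks but not 4 meets both the Cannot Monitor row and the 5-8xULN row. That looks like a third contradiction and is not one. Both monitoring rows direct the site to the stopping actions whenever a stopping criterion is met, and Section 8.1.1 says treatment is then discontinued. The same rule resolves all 230 overlapping grid states.

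**Path-dependent reading of (b).** The step-down may be meant for anyone who entered through the 5-8xULN row, and 14-day checks can still show persistence at 4 weeks. This is plausible, but it is not written.

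**Flowchart.** The Section 8.1.1 algorithm is not shown in the available text and may route the gap case. If it does, the Appendix 4 tables still need to agree with it.

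**Conclusion.** Both points hold on the text of Appendix 4.

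(a) The gap is narrow: first detection, ALT ≥3 and <8xULN, bilirubin ≥2xULN, a measured direct fraction of 35% or less, INR not above 1.5, no symptoms and weekly monitoring possible. Calling it mainly indirect bilirubin would be too broad, since 36-49% direct is also mainly indirect and is a stopping event. Within the gap, chemistry with higher bilirubin has less mandated action than chemistry with lower bilirubin, and whether treatment stops depends on how quickly a fraction is available.

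(b) The conflict is between checks about 14 days apart and checks 7 days apart, for ALT still at 3 to <5xULN after week 2.

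Numbers affected are probably small, and no rate is given. The conclusion assumes that the tables are read as written and that the unseen flowchart does not override them. This is an inconsistency in a stated safety rule, more than missing detail, and should be corrected.

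**What to change.** Reconcile the two Appendix 4 tables, footnote 1 and the Section 8.1.1 algorithm so that every combination of ALT ≥3xULN with bilirubin level and direct fraction (measured or unavailable) has one stated action, including participants admitted under the Gilbert's and isolated-bilirubin exceptions. Reconcile the week-2 step-down of the 5-8xULN row with the 3-5xULN row, and say which row governs a participant who moves between bands. The sponsor decides which action and frequency apply; this review proposes neither. The cost is a wording amendment and possibly a few extra liver tests in rare participants.
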